7.2 Data Analysis Plan

The main hypothesis test will be performed as described above. Subgroup analyses to compare PFS between patients with ≤ 10 pack years vs patients with > 10 pack years (but with no p53 mutation) smoking history will be conducted using log-rank test. Additionally, a Kaplan-Meier curve will be estimated for PFS, local control, regional control, local-regional control, distant metastasis free survival and overall survival. Circulating free HPV DNA before, during, and after CRT will be compared, using the paired t-test or McNemar's test as appropriate. As an exploratory analysis, joint modeling of longitudinal cfHPV-DNA and time-to-progression will be conducted to examine the association between time-varying cfHPV-DNA and disease progression. We will also perform exploratory analyses of the other genetic alterations that are assessed by the TruSight Tumor Panel® and fluorescent in-situ hybridization studies.

In addition to the above, other exploratory analyses utilizing study-related data may be performed. These analyses will be consistent with the overarching aims of the study.

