1.4 Prospective Clinical Data on HPV positive HNSCC

Numerous retrospective studies have shown that patients with HPV-positive HNSCC have a significantly better prognosis than patients with HPV-negative HNSCC^{5,25,29}. These preliminary data have been verified in analyses of prospective clinical trials^{10,13,18}. Fakhry et al. evaluated the HPV status of 96 patients with laryngeal or oropharyngeal SCC from an Eastern Cooperative Oncology Group (ECOG) phase II trial. Patients with HPV positive tumors had higher response rates after induction chemotherapy (82% vs. 55%, p = 0.01) and CRT (84% vs. 57%, p = 0.007) as compared to those with HPV-negative tumors. The 2 year overall survival was also improved - 95% (HPV positive) vs. 62% (HPV negative). Lassen et al. analyzed the Danish Head and Neck Cancer Group (DAHANCA) 5 trial and observed an improved local-regional control, disease specific survival, and overall survival in patients whose tumors were p16 positive (a surrogate marker for HPV) versus those who were p16 negative¹⁸.

The RTOG 0129 prospective randomized trial also validated HPV positivity as being a strong, independent prognostic factor for overall and progression free survival¹⁰. RTOG 0129 compared accelerated fractionation radiotherapy with standard fractionation, both with concurrent cisplatin (2 cycles in the former and 3 cycles in the latter). There was no statistical difference in overall or progression free survival between the two arms. Post-hoc analysis of HPV status and outcomes in the OPSCC subset showed a significant improvement in OS (82.4%, vs. 57.1% at 3 year; P<0.001) and PFS in the HPV positive tumors. After accounting for other prognostic factors, HPV positivity conferred a 58% reduction in the risk of death (hazard ratio, 0.42; 95% CI, 0.27 to 0.66). Locoregional control was improved in the HPV-positive tumors; however, distant metastatic control and the rate of second malignancies were similar for both HPV-positive and negative OPSCC subgroups. Through recursive portioning analysis this OPSCC cohort was stratified into low, intermediate, and high risk groups for death (3 year OS of 93%, 70.8%, and 46.2% respectively). The factors used for stratification, in order of importance, were: HPV status, pack-years of tobacco smoking, tumor stage, and nodal stage. To be categorized as having low risk of death, a patient must have a HPV-positive

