tumor and either have \leq 10 pack years of tobacco smoking and any N stage or >10 pack years of tobacco smoking and N0-N2a nodal stage.

O'Sullivan et al. conducted a large retrospective study of 899 OPSCCs patients treated at the Princess Margaret Hospital in Toronto, Canada³². HPV status was ascertained in 505 (56%): 382 HPV positive and 123 HPV negative. All patients were treated with radiation alone or CRT from 2001 to 2009, with a median follow-up of 3.9 years. Recursive portioning analysis segregated HPV-positive patients into low (T1-3 N0-N2c) and high (T4 or N3) distant metastasis risk: 93% vs. 76% respectively. Furthermore, smoking > 10 pack years reduced overall survival but did not impact recurrence free survival (local, regional, and distant recurrences) in HPV-positive patients. This suggests that other associated tobacco-related disease may be the reason for decreased survival in HPV-positive smokers vs. HPV-positive non-smokers. Also, the recurrence free survival was excellent (>90%) in low-risk HPV-positive patients with T1-2, N0-1 disease treated with RT alone vs. CRT. Thus the addition of chemotherapy to radiation in this very favorable low-stage subset may not be necessary.

An unanswered question is whether we can safely de-intensify in patients with HPV-associated OPSCC who have significant smoking histories (> 10 pack years). The proposed study will help to answer this question.

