2.0 STUDY OBJECTIVES

2.1 Primary Objective:

To evaluate whether genomic based risk-stratification can be used in deciding whether to de-intensify in patients with HPV-associated OPSCC with > 10 pack years smoking history. Hypothesis: Patients with HPV-associated OPSCC, > 10 pack years smoking history, and non-mutated p53 will have similar 2 year PFS as patients with < 10 pack years smoking history.

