4.0 PATIENT ELIGIBILITY

4.1 Inclusion Criteria

- 4.1.1** ≥ 18 years of age (no upper age limit)
- 4.1.2** T0-3, N0 to N2c, M0 squamous cell carcinoma of the oropharynx (AJCC 7th edition)
- 4.1.3** Biopsy proven squamous cell carcinoma that is HPV and/or p16 positive
- 4.1.4** Radiologic confirmation of the absence of hematogenous metastasis within 12 weeks prior to treatment; at a minimum, chest x-ray is required. CT imaging of the chest or PET/CT is acceptable.
- 4.1.5** ECOG Performance Status 0-1
- 4.1.6** CBC/differential obtained within 8 weeks prior to treatment, with adequate bone marrow function defined as follows:
 - 4.1.6.1** Platelets $\geq 100,000$ cells/mm³
 - 4.1.6.2** Hemoglobin ≥ 8.0 g/dl (Note: The use of transfusion or other intervention to achieve Hgb ≥ 8.0 g/dl is acceptable.)
- 4.1.7** Adequate renal and hepatic function within 4 weeks prior to treatment, defined as follows:
 - 4.1.7.1** Serum creatinine < 2.0 mg/dl
 - 4.1.7.2** Total bilirubin $< 2 \times$ the institutional ULN

4.1.7.3 AST or ALT < 3 x the institutional ULN.

Note that physician attestation of patient having no known history of liver disease can take the place of bilirubin and AST/ALT labs.

- 4.1.8** Negative pregnancy test within 2 weeks prior to treatment for women of childbearing potential
- 4.1.9** Women of childbearing potential and male participants who are sexually active must practice adequate contraception during treatment and for 6 weeks following treatment.
- 4.1.10** Patients must be deemed able to comply with the treatment plan and follow-up schedule.
- 4.1.11** Patients must provide study specific informed consent prior to study entry

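### The PFS comparison between smoking groups is not stratified by nodal stage, so an unequal nodal mix could mask or exaggerate a difference

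*Combined protocol and SAP*

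**What the plan says.** Section 2.1 states the hypothesis that patients with more than 10 pack years and "non-mutated p53 will have similar 2 year PFS as patients with < 10 pack years smoking history". Section 7.2 addresses it with one analysis: PFS in lighter smokers "vs patients with > 10 pack years (but with no p53 mutation) smoking history will be conducted using log-rank test". It is called a subgroup analysis. No stratification factor, covariate, significance level or power is given for it. The formal test in section 7.1 is a one-sample binomial test on the whole cohort and does not compare smoking groups.

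Section 4.1 admits "T0-3, N0 to N2c, M0 squamous cell carcinoma of the oropharynx (AJCC 7th edition", with no link between nodal stage and smoking history. Section 5.4 uses p53 alone to risk stratify.

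Section 1.4 describes a partitioning model from a cited randomised trial. Its factors, "in order of importance, were: HPV status, pack-years of tobacco smoking, tumor stage, and nodal stage", produce groups "stratified into low, intermediate, and high risk groups for death (3 year OS of 93%, 70.8%, and 46.2% respectively". An HPV-positive patient is low risk with 10 or fewer "pack years of tobacco smoking and any N stage or >10 pack years of tobacco smoking and N0-N2a nodal stage". So nodal stage divides patients with more than 10 pack years, but not lighter smokers.

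**The concern.** Smoking history is a patient characteristic, so the two groups may differ in nodal stage at entry. If nodal stage also affects PFS, an unstratified log-rank test mixes its effect with that of smoking. Heavier smokers with less advanced nodes would look better than a like-for-like comparison shows. With more advanced nodes they would look worse, or appear to differ when smoking has no effect.

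At stake is the reading of the hypothesis in section 2.1, because no other planned analysis addresses it. Nodal stage is the natural factor to control: the protocol's background names it as a divider of risk in this group, and it is already recorded for eligibility.

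**Working it through.** **The plan's own figure.** Section 7.1 gives no power for the log-rank test. For the main test it states n = 225 (250 × 0.90), rejection at 23 or more failures, and rejection probabilities of 0.045 at PFS 0.93 and 0.96 at PFS 0.86. The exact values are P(X ≥ 23 | 225, 0.07) = 0.0446 and P(X ≥ 23 | 225, 0.14) = 0.963. Both reproduce. The point here does not affect that test.

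**Assumed inputs, none of them in the documents.**
- Of 225 patients, 30% have more than 10 pack years and no p53 mutation; the rest are lighter smokers.
- Two-year PFS in N0-N2a is 0.96 in both groups. In N2b-N2c it is 0.90 in lighter and 0.80 in heavier smokers.
- Times are exponential and censored at 2 years; tests are two-sided at 0.05; 4,000 simulated trials per row.

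**Formulas.** With m the share in N2b-N2c, pooled PFS = (1 − m) × PFS in N0-N2a + m × PFS in N2b-N2c. Crude hazard ratio = ln(PFS heavier) / ln(PFS lighter). The true ratio within N2b-N2c is ln 0.80 / ln 0.90 = 2.12; within N0-N2a it is 1.

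**Pooled values.**
- Heavier smokers less advanced (m = 0.30 against 0.60): heavier 0.7 × 0.96 + 0.3 × 0.80 = 0.912; lighter 0.4 × 0.96 + 0.6 × 0.90 = 0.924.
- Heavier smokers more advanced (m = 0.60 against 0.30): heavier 0.4 × 0.96 + 0.6 × 0.80 = 0.864; lighter 0.7 × 0.96 + 0.3 × 0.90 = 0.942.
- Equal mix (m = 0.50): heavier 0.880; lighter 0.930.

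| Nodal mix | Crude HR | Rejects, unstratified | Rejects, stratified |
|---|---|---|---|
| Heavier smokers less advanced | 1.17 | 6% | 21% |
| Heavier smokers more advanced | 2.45 | 50% | 20% |
| Equal | 1.76 | 26% | 27% |

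The expected number of events is 18 to 19 in each row.

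**No smoking effect, unequal mix.** Set N2b-N2c PFS to the same value in both groups.
- At 0.90, with heavier smokers more advanced, pooled PFS is 0.924 against 0.942 (crude HR 1.32). The false-positive rate is about 10% crude and 5% stratified. With the mix reversed it is about 6% and 4%.
- At 0.85, the rates are about 15% and 5% with heavier smokers more advanced, and about 9% and 5% with the mix reversed.

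**Smoker share.** With shares in N2b-N2c of 30% in heavier and 70% in lighter smokers, and the same PFS values as in the table, 1,500 runs gave 4% crude against 24% stratified at a 30% heavier-smoker share, and 6% against 19% at a 20% share.

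**Precision of the descriptive estimate.** If half of the heavier smokers are N2b-N2c, they number 225 × 0.30 × 0.50 ≈ 34. With 31 of 34 progression-free, the exact 95% interval is 76% to 98%.

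**The case against.** The strongest objection concerns the evidence. The model in section 1.4 was fitted post hoc to death in another trial; it is not a PFS model and this protocol does not adopt it. The same section reports a retrospective study in which more than 10 pack years did not affect recurrence-free survival in HPV-positive patients. That study also placed T1-3 N0-N2c in one low-risk group for distant metastasis, with no cut at N2a. This stands: that nodal stage divides PFS among heavier smokers is an inference.

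A reader might infer that N0-N2a smokers are already settled as low risk, so that only N2b-N2c smokers matter and pooling hides harm in them. The documents do not support that. Section 1.4 poses the open question for all patients with more than 10 pack years, and the hypothesis in section 2.1 has no nodal limit. The pooled group is therefore the stated target. Harm confined to N2b-N2c would be averaged over that group, but the averaging follows from the question asked.

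The gain also depends on imbalance. With an equal mix the two tests perform alike. Stratifying leaves power near 20% to 27% in the table, and the nodal-subgroup interval is wide. Finally, section 7.2 labels the comparison a subgroup analysis, attaches no decision rule to it, and allows further exploratory analyses. That allowance names no nodal analysis and so does not pre-specify one.

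What remains is the confounding: a non-randomised comparison that carries the hypothesis of section 2.1 leaves a recorded, plausibly prognostic factor uncontrolled.

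**Conclusion.** The point holds as a minor one. An unequal nodal mix can mask or exaggerate a PFS difference between smoking groups in the planned test. Under the stated assumptions, the same true effect is detected 6% or 50% of the time by the crude test depending only on the mix, against about 20% with stratification. With no smoking effect, crude false-positive rates reach about 10% to 15% when heavier smokers have more advanced nodes, against about 5%.

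These figures rest on an assumed smoker share, nodal mix and PFS by nodal stage. The actual direction and size are unknown, and the distortion vanishes if the groups have the same mix or if nodal stage does not affect PFS. It would go too far to say that the plan conceals harm in N2b-N2c smokers, or that the protocol's evidence establishes worse PFS for them: the cited model concerns death, and the recurrence evidence cited beside it shows no smoking effect.

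**What to change.** In section 7.2:
- Stratify the smoking-group log-rank test by nodal stage, N0-N2a versus N2b-N2c.
- Tabulate nodal stage by smoking group.
- Report 2-year PFS with a 95% confidence interval by nodal stage within the p53-non-mutated group with more than 10 pack years, labelled descriptive.
- State that a non-significant result is not evidence of similar PFS.

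The cost is analysis wording and one factor already on file; no new data or patients are needed. The limits are few events and wide subgroup intervals. Stratifying guards against nodal confounding only. Section 5.7 also ties chemotherapy to T and N stage and smoking history, so some treatment difference between smoking groups may remain within the N0-N2a stratum and should be described alongside the result.

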1.8 Rationale

The proposed study will build upon on our seminal prior phase II and genomic characterization studies by leveraging unique clinical/ translational strengths at UNC-LCCC: cancer genomics and cfHPV-DNA. Our over-arching hypothesis is that the

genomic characterization of OPSCC tumor specimens from patients with > 10 pack year smoking history can be used to help decide whether de-intensification would be efficacious.

Because of the positive results of our first two de-intensification studies (LCCC 1120, LCCC 1413) and the emerging genomic risk stratification data from [REDACTED] et al. and [REDACTED] et al., we are proposing conducting a similar study with the major modification of:

1. Tumor Genetics: Tumor genetics will be assessed in all patients with > 10 pack year smoking history, and select patients with extensive smokeless tobacco history, based on the PI's assessment. The UNC Molecular Genetics Laboratory will perform a mutation panel interrogating selected regions of 26 genes (p53 mutation is the most common to this patient population) using next-generation sequencing. P53 mutational status will be used to assess eligibility of patients with >10 pack years smoking history.
2. Circulating free HPV DNA: In this study we will prospectively collect blood samples pre-treatment, during, and after treatment to evaluate the kinetics of cfHPV-DNA in all patients.
3. Primary endpoint: Our hypothesis is that by using genomic profiling in the patients with HPV-associated OPSCC and > 10 pack year smoking history that we will be better able to select those patients with HPV-associated OPSCC who would safely benefit from de-intensification. The primary endpoint is PFS, however by using genomics to select the most favorable patients with a > 10 pack year smoking history, we estimate the PFS to be 93% (for the entire population, regardless of smoking), instead of the 87% as has been reported in previous studies¹⁰ and our prior studies.

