3.0 ENDPOINTS

3.1 Primary Endpoint

Patients with HPV-positive and/or p16-positive OPSCC will receive de-intensified CRT. The 2 year PFS will be evaluated. Our null hypothesis (H_0) is that the PFS rate is 93% and our alternate hypothesis (H_1) is that the PFS rate is 86%.

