5.0 STUDY PLAN

5.1 Schema

[figure not shown]

Figure 2: Schema

Figure 2: The primary objective of this study is to assess the 2 year PFS of HPV-associated OPSCC after genetic risk based de-intensified CRT. All patients with ≤ 10 pack years smoking history will receive de-intensified CRT. Patients with > 10 pack years smoking history, and select patients with extensive smokeless tobacco history (based on the PI's assessment), will have genetic assessment of their tumors (pre-treatment archival tissue or biopsies), and if p53 is mutated, they will receive an additional 10 Gy for a total radiation dose of 70 Gy (which is the historical, standard) and one additional weekly chemotherapy dose. Those with > 10 pack year smoking history and without the p53 mutation will receive the de-intensified regimen. Circulating free HPV DNA will be assessed pre-treatment, during treatment, and post-treatment at months 3, 6, 12, 18, and 24 (See Section 5.5 for details on blood collection time points).

5.2 Pretreatment Evaluations: All patients will have standard of care evaluation and staging procedures.

5.2.1 Complete history and physical exam including weight and performance status.

5.2.2 Completion of panendoscopy with directed biopsies and bilateral tonsillectomies if the primary is unknown is strongly recommended, but not required.

5.2.3 Completion of the following radiological studies:

at least contrasted neck CT and chest x-ray. Chest CT, PET/CT and/or MRI are optional studies. CT of the neck should have IV contrast unless contraindicated (allergy or adverse reaction or renal issues). PET/CT is satisfactory and can be done instead of or in addition to contrasted neck CT and chest x-ray. Pretreatment ultrasound evaluation with possible FNA is permissible to stage the neck prior to treatment.

5.2.4 Complete dental evaluation is recommended.

5.2.5 Completion of the following laboratory studies: CBC, serum chemistries, liver function tests, and pregnancy test if female.

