7.0 STATISTICAL CONSIDERATIONS

7.1 Study Design/Study Endpoints

The main objective of this Phase-II trial is to estimate the two-year progression-free survival probability (PFSP) in this group of patients treated with de-escalated radiotherapy. The planned total sample size is 80 patients. (This number was increased to 120 as of July 7, 2017, 140 as of February 7, 2019, 160 as of May 29, 2019, 180 as of October 9, 2019, 200 as of January 7, 2020, and 250 as of June 17, 2020. Please see details below.) The recruitment phase is expected to last 48 monthsDrop out is expected to be about 10%, based on a previous trial (LCCC 1120), hence we expect a total of 225 patients to complete the study.

The statistical aim is phrased as a hypothesis test with the null hypothesis being that the two-year PFSP is 0.93 and the alternative hypothesis being that the two-year PFSP is 0.86 (or less). A one sample binomial test will be used to assess this hypothesis. If the null hypothesis is rejected the conclusion will be that the de-escalated treatment is inferior to the standard treatment. If the null hypothesis is not rejected the conclusion will be that the de-escalated treatment is at least as good as the standard RT.

We give power calculations for two sample sizes. For a sample size of n=73 (patients who complete the study), the null hypothesis will be rejected if 11 or more patients fail. Failure is defined as not reaching the two-year time point progression-free. Defining P(Reject H0) to be the probability of rejecting the null hypothesis, the performance of the test is summarized in the following table.

True 2-year PFSP	P(Reject H0)
0.93	0.03
0.86	0.58
0.80	0.94
0.75	0.99

For a sample size of n=80 patients, the null hypothesis will be rejected if 12 or more patients fail. The performance of the test is summarized in the following table.

True 2-year PFSP	P(Reject H0)
0.93	0.02
0.86	0.57
0.80	0.94
0.75	0.99

For n=73 to 78, the critical point is 11 failures. For n=79 and 80, the critical point is 12 failures. With these critical points, type-I error ranges from 0.023 to 0.045 depending on sample size.

Sample size and power re-calculation: On July 7, 2017, the PI, noticing the higher than expected patient accrual rate, decided to increase sample size to 120. This should result in

about 108 patients to complete the study, after accounting for drop-out with an expected drop-out rate of 10%.

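### Section 2.1 makes similar PFS across smoking groups the primary hypothesis, but the primary test is one single-group rate and the only analysis of the contrast, a log-rank test, cannot show similarity

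*Combined protocol and SAP*

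**What the plan says.** Section 2.1, headed as the primary objective, asks whether genomic risk stratification can guide de-intensification in patients with more than 10 pack years. Its hypothesis compares two groups: those with "non-mutated p53 will have similar 2 year PFS as patients with < 10 pack years smoking history". It gives no margin and does not define similar.

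The other sections that name a primary quantity describe a single rate:

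- Section 3.1: "Patients with HPV-positive and/or p16-positive OPSCC will receive de-intensified CRT. The 2 year PFS will be evaluated", with 93% as the null and 86% as the alternative.
- Section 5.1: "The primary objective of this study is to assess the 2 year PFS of HPV-associated OPSCC after genetic risk based de-intensified CRT". Section 5.11 describes the endpoint the same way.
- Section 7.1: "The main objective of this Phase-II trial is to estimate the two-year progression-free survival probability (PFSP"), tested with a one-sample binomial test. At the current target of 225 completers the null is rejected at 23 or more failures. All sizing in 7.1 is for this test.

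Section 7.2 separates the two: "The main hypothesis test will be performed as described above. Subgroup analyses to compare PFS" by smoking history, in which "patients with > 10 pack years (but with no p53 mutation) smoking history will be conducted using log-rank test". It gives no significance level, sidedness, follow-up cut, expected group size or between-group interval. It also plans a Kaplan-Meier curve for PFS, but does not say that it will be drawn by group.

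**The concern.** Sections 1.1 and 1.4 present de-intensification in patients with a smoking history as the open question the trial should help to answer, and 2.1 turns it into the primary hypothesis. The statistical hierarchy is nonetheless clear: the one-sample test is primary, the smoking contrast is a subgroup analysis, and 2.1 is the outlier.

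The method for the contrast does not fit the hypothesis. A log-rank test takes equality as its null, so a non-significant result does not show that two groups are similar. It also compares whole curves, while 2.1 speaks of the 2-year rate. The pooled test does not help either, because it can accept while the wild-type group with more than 10 pack years does worse than the light smokers. The trial could therefore report a favourable primary result that is taken to support 2.1 when no planned analysis can support it.

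**Working it through.** **Reproducing the plan's figure.** Section 7.1, n=225, reject at 23 or more failures, exact binomial:

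- P(X ≥ 23 | 225, 0.07) = 0.0446 (plan: 0.045)
- P(X ≥ 23 | 225, 0.14) = 0.963 (plan: 0.96)

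Both agree.

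**Inputs for the contrast.** From 7.1: n=225, the 23-failure rule, and the 93% and 86% rates. Assumed, because the documents do not give them:

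- The wild-type group with more than 10 pack years is 20, 30 or 40% of 225, so light/wild-type counts are 180/45, 157/68 and 135/90.
- None of the 225 carries a p53 mutation (optimistic for group size).
- PFS times are exponential, and the log-rank test is two-sided at 0.05.

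**Pooled rule with light smokers at 93% and wild-type at 86%.** Expected failures = 0.07·n_light + 0.14·n_wt. P(accept) = P(total ≤ 22), from the convolution of two binomials.

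| Share | Expected failures | Pooled PFS | P(accept) |
|---|---|---|---|
| 20% | 12.6 + 6.3 = 18.9 | 0.916 | 0.81 |
| 30% | 10.99 + 9.52 = 20.5 | 0.909 | 0.69 |
| 40% | 9.45 + 12.6 = 22.05 | 0.902 | 0.55 |

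Expected failures stay below 23 throughout, so the pooled test accepts more often than not.

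**Log-rank power for 93% vs 86%.** HR = ln 0.86 / ln 0.93 = 2.08. Schoenfeld: power = Φ(√(d·s(1−s))·ln HR − 1.96), with d events and wild-type share s. At a 20% share cut at 2 years: d = 18.9, √(18.9 × 0.16) = 1.739, 1.739 × 0.732 = 1.272, and Φ(1.272 − 1.96) = 0.25. The 30 and 40% shares give 0.33 and 0.39.

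Section 7.2 sets no follow-up cut. Section 5.11 ends participation 2 years after CRT but continues routine follow-up; 5.12 schedules visits for 3 further years and then yearly. Whether later events count is open, so power is shown as a range over the 20–40% shares:

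| Follow-up | Simulated | Schoenfeld |
|---|---|---|
| 2 years | about 34–40% | 25–39% |
| 4 years | about 56–66% | 42–64% |
| 5 years | about 61–74% | 49–72% |

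Repeat simulations move these by a point or two. Simulated size with both groups at 93% and a 2-year cut is about 0.045, so the simulated figures are the better guide; Schoenfeld runs low with unequal groups and few events.

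**Larger deficit.** For 93% vs 80% cut at 2 years, simulated power is about 71, 80 and 83% at the three shares.

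**What an estimate would deliver.** 95% half-width for the 2-year difference = 1.96·√(p₁(1−p₁)/n_light + p₂(1−p₂)/n_wt). At a 20% share with both groups at 93%: 1.96·√(0.0651/180 + 0.0651/45) = 8.3 points.

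| Truth | 20% | 30% | 40% |
|---|---|---|---|
| 93% and 93% | 8.3 | 7.3 | 6.8 |
| 93% and 86% | 10.8 | 9.2 | 8.4 |

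**The case against.** The strongest reply is that nothing in the decision rule is broken. The hierarchy is stated, 7.2 already calls the comparison a subgroup analysis, and phase II subgroup comparisons often have no margin. That stands, and it limits the point to 2.1 and the treatment of one contrast.

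Four stronger readings are tempting and are not supported:

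- **That 2.1 can be neither supported nor contradicted.** The log-rank test compares essentially the groups named in 2.1 and can contradict the hypothesis when the deficit is large, as the 93% vs 80% figures show. What it cannot do is show similarity.
- **That the log-rank test simply has low power.** This holds at 93% vs 86% if follow-up stops at 2 years. With 4 or 5 years of events, power is moderate, and 7.2 does not exclude those events.
- **That the trial will read a non-significant log-rank result as similarity.** The protocol does not say so. Section 7.1 draws a favourable conclusion from non-rejection, but only for its own one-sample test.
- **That the documents contradict each other on the primary population.** Section 1.8 says "we estimate the PFS to be 93% (for the entire population, regardless of smoking"), while 3.1, 5.11 and 7.1 speak of patients given de-intensified treatment. The wording in 1.8 spans smoking strata and does not mention p53-mutated patients. Whether those patients count in the pooled test deserves a sentence, but it is a separate and smaller clarification.

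**Conclusion.** The concern holds in a limited form. Section 2.1 is out of line with the rest of the plan, and the one analysis of its contrast can reveal a large deficit but cannot show similarity and does not target the 2-year rate. The pooled rule accepts with probability 0.55 to 0.81 when the wild-type group is 7 points worse, the protocol's own gap between null and alternative. Log-rank power for that gap runs from about 34% to about 74% by simulation, depending on group share and follow-up.

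These figures rest on assumed shares of 20–40%, exponential PFS, no p53-mutated patients among the 225 and a two-sided 0.05 level. That a log-rank test cannot establish similarity depends on none of them. The matter should be fixed before the comparison is analysed, but it does not undermine the primary test.

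**What to change.** 1. Align 2.1 with 7.1: make the 2-year PFS rate the primary objective and label the smoking comparison secondary and descriptive. Use one pack-year cut-off; 2.1 has < 10 where 7.2 has ≤ 10.
2. In 7.2, report the Kaplan-Meier 2-year PFS difference (more than 10 pack years with wild-type p53, minus light smokers) with a 95% confidence interval, and the wild-type group's own 2-year PFS with its interval. Limit both groups to patients assigned the de-intensified regimen. As written, 7.2 removes p53-mutated patients only from the group with more than 10 pack years, yet under 5.1 "select patients with extensive smokeless tobacco history (based on the PI's assessment), will have genetic assessment of their tumors", and some of these may have 10 pack years or fewer. If the log-rank test is kept, state its follow-up cut and that a non-significant result is not evidence of similarity.
3. If a similarity claim is kept, the sponsor should set and justify a margin before the comparison is run.

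**Cost.** No new patients or data are needed, since 7.2 already plans Kaplan-Meier estimation. The conclusion becomes less definite: the interval is about ±7 to ±8 points if the groups are equal and ±8 to ±11 if they differ by 7. A margin would be demanding. Purely as an illustration, with 7 points and identical groups at 93%, Φ(0.07/SE − 1.645) with SE = 0.0425, 0.0370 and 0.0347 gives only about 50, 60 and 64% chance of excluding it at one-sided 0.05. This is a late change to a single-arm trial, so it should be dated and disclosed, with a statement of whether outcomes had been seen.
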